1.2 Primary Study Endpoints

The primary efficacy measure is the proportion of participants that achieve HiSCR (is the total number of abscess and inflammatory count of the participants lesions) at Week 16 with topical ruxolitinib 1.5% cream as compared to Baseline (Week 0). The HiSCR is defined as at least a 50% reduction in the total abscess and inflammatory nodule count (AN count) for all study body sites with no increase in abscess count and no increase in draining fistula count relative to Baseline. The primary efficacy analysis will be carried out on all participants who complete 16 weeks of treatment.

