3.0 Inclusion and Exclusion Criteria

3.1 Inclusion Criteria

1. Male or female subjects age 12 years or older
 - This inclusion criteria has been updated due to the approval of the study medication for use in this age group (12 years and older) in other indications. Additionally, Humira, an approved biologic medication for HS, is also used in this population, highlighting the need for topical breakthrough treatments for those affected by HS at younger ages. Due to the open-label nature of this medication and the anticipated benefits for any children participating, the greater than minimal risk of this study design is justified.
2. Hidradenitis suppurativa, and should be Hurley Stage I or II, defined as papules, nodules, and/or abscess formation, single or multiple, with or without sinus tracts;
3. Subjects must have a diagnosis of HS for at least 3 months (90 days) prior to Baseline;
4. Active HS lesions must be present in at least one distinct anatomic area;

5. Subject must have at least 3 total inflammatory lesions at the Baseline visit;
6. Subjects who had surgery in the treatment area, should be at least 3 months status post the procedure (this applies to deroofting/marsupialization or excision, not incision & drainage)
7. Subject has a negative TB screening assessment (including a PPD test and/or T-Spot) OR for patients with treated latent TB or negative chest x-ray (CXR posterior-anterior [PA] and lateral view within prior 90 days) at Screening with documentation of treated latent tuberculosis (90 days of treatment).
8. Medications can be continued if they have been at a stable dose for the requisite duration and the dose is not increased during the study period:
 - Biologic medication (such as TNF α , IL-12/23 or IL-17 inhibitors): Up to 30% of enrolled participants will be allowed to remain on a concurrent biologic at stable dosage if treated with a stable dose and frequency for 6 months or longer;
 - Oral antibiotic must be a stable dose and frequency for 28 days or longer;
 - Hormone-based therapy (birth control pills or spironolactone) must be a stable dose and frequency for 4 months or longer;
 - Oral retinoids must be on a stable dose and frequency for 90 days or longer;
 - Other topical therapy must be discontinued 14 days prior to the Baseline visit.

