7.3 Duration of Participation

During the study, participants will have scheduled visits in the Dermatology Research Office at Screening, Baseline/Week 0 (can be combined with Screening), Week 4, Week 8, and Week 16. Each of these visits is expected to last for up to 60 minutes.

Participation will be up to 24 weeks long, including the screening and follow up periods.

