In the event of an acutely painful lesion that requires immediate intervention, the investigator and participant will have the option to perform protocol-allowed interventions. Two types of interventions are permitted: injection with intralesional triamcinolone acetonide suspension (up to 40 mg in total at the same visit) and/or incision and drainage. New systemic and topical therapies following incision and drainage, including antibiotics, are prohibited. Participants should continue using the topical study therapy. From Day 1 through Week 16, an intervention can occur on a maximum of 2 different lesions at the same visit or on the same lesion at 2 different study visits. The same lesion cannot be treated 2 times during the same visit. If participants require more than 3 interventions before Week 16, then the study drug will be discontinued for those participants. Study procedures must be performed before any interventions. Any lesion undergoing an intervention will be documented in the lesion count worksheet.

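### HiSCR as written counts a Baseline lesion that was injected or drained and is absent at Week 16 as a reduction, so a rescue effect can be credited to the cream

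*Combined protocol and SAP*

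**What the plan says.** Section 1.2 defines the primary endpoint as "at least a 50% reduction in the total abscess and inflammatory nodule count (AN count) for all study body sites", together with "no increase in abscess count and no increase in draining fistula count relative to Baseline". Nothing in the definition refers to rescue.

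Section 7.4.6.5 permits two procedures for an acutely painful lesion: "injection with intralesional triamcinolone acetonide suspension (up to 40 mg in total at the same visit) and/or incision and drainage". On timing and number it says "From Day 1 through Week 16, an intervention can occur on a maximum of 2 different lesions at the same visit", or the same lesion at two visits. Study drug stops after more than three interventions, but no response status follows from that. Two sentences bear on the data: "Study procedures must be performed before any interventions" and "Any lesion undergoing an intervention will be documented in the lesion count worksheet".

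Section 8.3 provides last observation carried forward for missing data and does not mention rescue. Section 7.2.1 collects rescue use in the weekly surveys, but no analysis uses it. Section 7.3 schedules visits at Screening, "Baseline/Week 0 (can be combined with Screening), Week 4, Week 8, and Week 16". Section 3.1 sets the entry burden: "Subject must have at least 3 total inflammatory lesions at the Baseline visit".

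**The concern.** The permitted procedures act directly on the abscesses and nodules that HiSCR counts. A Baseline lesion drained at Week 4 or Week 8 and gone at Week 16 is observed as absent. It is not missing, so the missing-data rule does not apply, and the endpoint computed as written takes it as a reduction.

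Assessing before intervening protects only the count at the visit where the rescue is given. It does not protect the Week 16 count after an earlier rescue. There is no control arm in which rescue could produce the same effect, there is no blinding, and the decision to rescue lies with the investigator and participant. Because entry needs only three inflammatory lesions, one or two rescued lesions can be a large share of a participant's count. A participant can then be a responder with little or no help from the cream.

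**Working it through.** **Which rescues create a reduction**

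- Baseline lesion rescued before Week 16 and absent at Week 16: yes. The rescue is normally at Week 4 or 8, since no visit is scheduled between Weeks 8 and 16. A Week 8 rescue must hold for 16 − 8 = 8 weeks.
- Lesion rescued at the Week 16 visit: no, because the count comes first.
- Lesion new since Baseline: no. Clearing it only restores the earlier count.

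**Per participant**

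Lesions that must clear for a 50% reduction = AN − floor(AN/2), where AN is the Baseline count.

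| Baseline AN | Must clear | Left for the drug after 1 rescued | After 2 rescued |
|---|---|---|---|
| 3 | 3 − 1 = 2 | 1 | 0 |
| 4 | 4 − 2 = 2 | 1 | 0 |
| 5 | 5 − 2 = 3 | 2 | 1 |
| 6 | 6 − 3 = 3 | 2 | 1 |

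Two rescued Baseline lesions, which one visit allows, meet the 50% component alone at AN 3 or 4. They must stay resolved, no new lesions may offset them, and abscess and draining fistula counts must not rise. The three entry lesions need not all be abscesses or nodules, so a Baseline AN below 3 is also possible.

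**Trial level**

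Inputs from section 8.2: n = 18 completers, null rate 20%, design rate 55%, type I error 5%, power 80%, reject at 5 or more responders. The number of converted non-responders (0, 1 or 2) is an assumption.

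Formula: P(X ≥ r) = Σ C(18, x) pˣ (1 − p)^(18 − x), summed over x = r to 18.

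The plan's own rule, r = 5, gives P(X ≥ 5 | 0.20) = 0.284 and P(X ≥ 5 | 0.55) = 0.995. It does not hold 5%. That is a separate problem. To isolate the rescue effect I use the smallest cutoff that does hold one-sided 5%:

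- P(X ≥ 7 | 0.20) = 0.0513, above 0.05
- P(X ≥ 8 | 0.20) = 0.0163, so the cutoff is 8

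If k non-responders are converted, the test is passed when the unaided count reaches 8 − k.

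| Converted | P(reject), 20% rate | P(reject), 55% rate | Verdict changed at 55% |
|---|---|---|---|
| 0 | P(X ≥ 8) = 0.0163 | 0.8720 | – |
| 1 | P(X ≥ 7) = 0.0513 | 0.9463 | 7.4% |
| 2 | P(X ≥ 6) = 0.1329 | 0.9817 | 11.0% |

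A milder assumption fixes k participants as responders whether or not they would have responded anyway. It gives 3.8% (k = 1) and 8.2% (k = 2) at the 20% null. If instead rescue converts a share q of non-responders, the apparent rate is 0.20 + 0.80q: 24%, 28% or 36% for q = 5%, 10% or 20%, and P(X ≥ 8) is 4.6%, 10.1% or 30.3%.

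Each conversion adds 1/18 = 5.6 percentage points to the response rate.

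**The case against.** - **The worksheet is not in the documents.** It may contain a counting convention, which cannot be ruled out. But sections 1.2 and 8.3, which define the endpoint and its analysis, do not state or cite one.
- **Silence can be read as a treatment-policy choice:** count whatever is there at Week 16. That is a legitimate estimand, but the plan does not claim it, and without a control arm it measures cream plus rescue while the stated aim is the effect of the cream.
- **The benchmark is external.** The documents do not say how the trials behind the placebo rates counted rescued lesions, so the bias against 20% could be smaller or larger than shown. If they counted as this plan literally does, a stricter rule makes the comparison less like-for-like. This stands, and it is a reason to report both analyses.
- **The cutoff of 8 is not the plan's.** Under 5 of 18, one or two conversions at 55% change the verdict with probability of only about 0.4% or 0.5%. At the 20% null, rejection goes from 28.4% to 49.9% or 72.9%. The small change at 55% reflects a rule that already rejects almost always.
- **Stand-alone conversion needs several conditions together,** and some worsening participants may withdraw under section 3.3.1 and not be completers. This limits how often it happens. It does not settle how to count when it does.

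**Conclusion.** The concern holds. Computed exactly as section 1.2 defines it, HiSCR credits the drug with a Baseline lesion removed by injection or drainage before Week 16, and neither section 7.4.6.5 nor section 8.3 prevents this. The gap in the text is certain, subject only to whatever the unseen worksheet may say. The per-participant effect is large at low counts: at AN 3 or 4, two rescued lesions can replace the whole 50% requirement and one can halve it.

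The trial-level effect is unknown, because the documents give no rescue rate. The rise from 1.6% to 5.1% or 13.3% rests on one or two assumed conversions and on a cutoff of 8. It shows sensitivity in a trial of 18 and is not a forecast. The plan should be corrected before the data are analysed.

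**What to change.** Add to sections 1.2 and 8.3:

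1. From its first injection or drainage, a lesion is counted once as present, at its pre-intervention type, at every later visit including Week 16.
2. A sensitivity analysis classes any participant who received a lesional intervention as a HiSCR non-responder.
3. The numbers of rescued participants and rescued lesions are reported.

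The cost is a few sentences. The sample size does not change. No new data collection is needed, since counts precede interventions and rescued lesions are already recorded. The sponsor should confirm that the worksheet identifies each rescued lesion and its type, so that a recurrence is not counted twice.

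The rule is deliberately conservative:

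- A lesion the cream would have cleared anyway stays in the count.
- At AN 4 with two rescued Baseline lesions, the other two must both clear. At AN 3, two lesions carried forward exceed the one allowed at Week 16, so that participant cannot respond.
- A new abscess drained at Week 4 or 8 remains an abscess at Week 16 and, if no Baseline abscess has resolved, fails the abscess criterion on its own.

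Each participant affected in these ways can lower the response rate by 5.6 percentage points among 18. If the sponsor prefers to keep the literal count as primary, it should say so, describe the result as cream plus permitted rescue, and still adopt items 2 and 3.

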8.0 Subject Numbers and Statistical Plan

8.1 Number of Subjects

We aim to enroll at least 18 subjects to complete the interventional study to assess the primary endpoint. Anticipating screen failures and loss-to-follow-up we anticipate screening and enrolling approximately 24 people with hidradenitis suppurativa. No additional participants with *any* biologic use will be enrolled after 30% of participants with stable dosage and frequency of a biologic are enrolled.

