8.2 Sample size determination

Based on the placebo and effect responses for adalimumab in the PIONEER trials (Kimball, 2016) for moderate-to-severe HS, the HiSCR response rate in the placebo group was approximately 27% (26.0% and 27.6%) and HiSCR rates of 42-59% for adalimumab. In mild-to-moderate and moderate-only HS treated with apremilast, the placebo HiSCR rate was 0% and in the response rate in the intervention groups was 53-55% (Kerdel 2019, Vossen 2019).

With a sample size of at least 18 participants, we will have sufficient power to determine if the HiSCR response rate for topical ruxolitinib 1.5% cream is 55% and significantly different from a 20% (or lower) placebo response rate with a power of 80% and risk of type I error of 5%. Typically, in a Simon's two-stage design, 11 patients would be accrued in the first stage and 7 additional in the second phase; however, we will accrue all in one cohort of at least 18 completed participants. The null hypothesis will be rejected if 5 or more responses are observed in 18 completed participants.

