8.3 Statistical methods

The PI cannot be involved in the primary data analysis, but can maintain involvement in the data interpretation required for authorship. The primary statistical analysis to evaluate the null hypothesis that the proportion of participants that achieve HiSCR at Week 16. P-values ≤ 0.05 will be considered significant. The primary efficacy analysis will be carried out in the ITT Population, defined as all patients who complete the study. Last-observation-carried-forward will be used for missing data.

Secondary endpoints include the mean change in the AN count at Week 16; mean change in DLQI score from Baseline to Week 16; mean change in the novel clinician-reported outcome measure (HASI, investigator-supplied) score from Baseline to Week 16; mean change in novel HS patient-reported outcome measure (HiSQOL, Investigator-supplied) from Baseline to Week 16. Secondary efficacy variables will be summarized in the ITT Population. Statistical tests from laboratory assays will be done with the assistance of Penn State biostatisticians. Analyses can include paired t-tests, repeated measure ANOVA and regression-based analyses depending on the number of replicates, samples and repeated measures captured during each assay.

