9.0 Data and Safety Monitoring Plan

9.1 Periodic evaluation of data

Data will be entered in REDCap for each participant's visit. Data reported entered into the REDCap data capture forms will be transcribed from source documents

and must be consistent with the source documents or the discrepancies will be explained. Patient Reported Outcomes will be reviewed at each scheduled visit. Safety data will be reviewed on an ongoing basis. Endpoint data will be reviewed periodically and at the end of the study. The Penn State College of Medicine Department of Public Health Sciences Clinical Trial Monitoring unit will oversee study monitoring according to the established Monitoring Plan.

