9.2 Data that are reviewed

The PI, Sub-Is, and study team will review and identify adverse events. The sponsor will also review any identified AEs. Study team members will input all data into RedCap and will review input Patient Reported Outcomes. PI and Sub-Is will evaluate eligibility and ensure the integrity of all clinician assessments. Study statisticians may conduct reviews of study data periodically to evaluate the endpoints or perform data quality checks.

The PI will conduct a regular review of the ongoing study with study staff members.

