9.6 Frequency of review of cumulative data

Cumulative data will be reviewed once after data is collected on all participants.

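### The success count of 5 is defined only for 18 completers and misses the stated 5% error even there, while the number of completers is open-ended and the sections on interim endpoint review conflict

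*Combined protocol and SAP*

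**What the plan says.** **Number of participants.** Section 8.1 states: "We aim to enroll at least 18 subjects to complete the interventional study to assess the primary endpoint". It expects to screen and enrol about 24 people, a figure that allows for both screen failures and loss to follow-up. Section 8.2 again describes a single cohort with 18 completers as a minimum. Neither section gives a maximum, a closing date or a rule for closing enrolment.

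**Success rule.** Section 8.2 takes a 55% HiSCR rate as the target and says that it would be "significantly different from a 20% (or lower) placebo response rate with a power of 80% and risk of type I error of 5" per cent. The decision rule is: "The null hypothesis will be rejected if 5 or more responses are observed in 18 completed participants". No count is given for any other number. Section 8.3 adds "P-values ≤ 0.05 will be considered significant", but names no test for the primary endpoint and does not say whether it is one-sided or two-sided.

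**Review during the trial.** Section 9.1: "Endpoint data will be reviewed periodically and at the end of the study". Section 9.2: "Study statisticians may conduct reviews of study data periodically to evaluate the endpoints or perform data quality checks". Section 9.6: "Cumulative data will be reviewed once after data is collected on all participants".

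**Setting.** The trial is open-label (Section 3.1), has no blinding (Section 7.4.5) and runs at one site (Sections 15.1 and 17). Clinician lesion counts, from which HiSCR is derived, are taken at Weeks 4, 8 and 16.

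**The concern.** With no comparator, the efficacy claim rests on one proportion and one threshold. That threshold has to match the number analysed and hold the stated error. Here it is tied to 18, while the plan allows more than 18 to complete. A fixed count becomes easier to reach as the denominator grows. It also has to be right at 18, and 5 of 18 is an observed rate of 27.8%, close to the placebo rate of about 27% that Section 8.2 itself cites from the adalimumab trials.

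The second issue is the denominator. If the people who run the trial can see responses accumulate, and nothing fixes when enrolment closes, a reader cannot be sure that the final number was chosen independently of the results. The sections that should settle this disagree with one another.

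**Working it through.** **Inputs.** Null rate 20%, target rate 55%, power 80%, type I error 5%, success at 5 or more of 18 (Section 8.2). At least 18 completers, about 24 screened and enrolled (Section 8.1). Sidedness is not stated, so one-sided 5% is used, with an upper tail of 2.5% as a check. Responses are taken as independent. All 24 completing is an upper bound, because the 24 includes screen failures and losses.

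**Step 1: the plan's own figure.** P(X ≥ 5), X ~ Binomial(18, 0.20) = 1 − (0.0180 + 0.0811 + 0.1723 + 0.2297 + 0.2153) = 1 − 0.7164 = 0.2836.

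The type I error is 28.4%, and power at 55% is 99.5%. The stated 5% and 80% are not reproduced. The combination of 11 + 7 = 18 with success at 5 or more does match the Simon minimax design for 10% against 35% (error 2.7%, power 80.05%). The count therefore fits a different pair of rates from the pair in the plan.

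**Step 2: the smallest valid count at 18.** P(X ≥ 7) = 5.13%, which just misses 5%. P(X ≥ 8) = 1.63%, with power 87.2%. So 18 completers are enough, but the cut-off is 8. It is 8 under a 2.5% upper tail as well.

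**Step 3: other completer numbers** (null 20%, exact, one-sided 5%).

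| Completers | Error if 5 is kept | Matched cut-off | Its error | Its power at 55% |
|---|---|---|---|---|
| 18 | 28.4% | 8 | 1.6% | 87.2% |
| 20 | 37.0% | 8 | 3.2% | 94.2% |
| 22 | 45.7% | 9 | 2.0% | 93.8% |
| 24 | 54.0% | 9 | 3.6% | 97.3% |

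With a 2.5% upper tail, the cut-off at 24 is 10 (error 1.26%, power 93.5%).

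**Step 4: closing at the first favourable result.** The worst case is a look after every completer from 18 to 24, stopping at the first success, by exact recursion at a true rate of 20%.

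- Matched one-sided cut-offs 8, 8, 8, 8, 9, 9, 9: cumulative error 1.63%, 2.33%, 3.21%, 4.31%, 4.31%, 4.57%, 5.08%. The mean reported response rate is 20.2%.
- Matched 2.5% upper-tail cut-offs: 3.0% by 24.
- Two looks only, at 18 (cut-off 8) and 24 (cut-off 9): 3.9%.
- A count of 8 held fixed at every size: 1.63%, 2.33%, 3.21%, 4.31%, 5.61%, 7.15%, 8.92%.

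The last line equals the single-look error for 8 or more at each size, because a count once reached stays reached. The excess there comes from a fixed count on a growing denominator and arises even without interim looks.

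**Step 5: the review sections side by side.** Section 9.1 commits to periodic endpoint review. Section 9.2 permits periodic evaluation of endpoints by statisticians. Section 9.6 allows one cumulative review, after all data are in. Read literally, the first two cannot both stand with the third.

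**The case against.** **A reader might infer that leavers are replaced until 18 complete.** The documents do not say so. Section 8.1 describes ordinary over-enrolment, set in advance, and has no replacement rule.

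**A reader might infer that the trial is set up to stop on a good run.** The documents do not support that either. Section 8.2 sets aside the two-stage form for one cohort, Section 9.6 has one cumulative review, Section 18.7 plans no stopping rules, and Section 8.3 keeps the PI out of the primary analysis. Section 9.2 is permissive and mentions data quality checks in the same sentence. Because the endpoint falls at Week 16, many looks would come too late to affect enrolment; the documents give no accrual rate to settle this. With matched cut-offs, even the worst case gives 5.1%, essentially the nominal level, and a bias of 0.2 percentage points.

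**The count of 5 is expressly limited to 18, and Section 8.3 supplies a p-value criterion usable at any number.** That is fair, so the 37.0% and 54.0% are conditional on carrying the count over. But no test is named, and at 18 the two rules disagree: 5, 6 or 7 responders succeed under Section 8.2, while their exact one-sided p-values are 0.284, 0.133 and 0.051.

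What stands against the plan is the wrong threshold at 18, the absence of a rule for any other number, the missing closing rule, and the conflict over review. Section 18.7 justifies its statement by safety, so it does not fix when enrolment closes. Section 8.3 excludes the PI from the analysis, but not from lesion assessment or enrolment decisions.

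**Conclusion.** The point holds in this form. The success rule does not deliver the stated 5% error against a 20% null: it is 28.4% at exactly 18 completers, and this is the largest part of the problem. It does not depend on open enrolment or interim review. The open-ended number adds to it, since no rule exists for 19 or more completers and carrying 5 over would give up to 54.0% at 24. Correcting the count to 8 without tying it to the number analysed would still let the error rise to 8.9% by 24.

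The interim-review issue is a conflict in wording plus a missing safeguard, not a planned stopping mechanism. Its quantified effect is small once the cut-offs are matched.

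These results assume a true null rate of exactly 20%, independent responses, 24 completers as the extreme upper end and, for the sequential figures, a look after every completer. The documents give no frequency of review.

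**What to change.** - **Section 8.2:** replace the fixed count with an exact binomial test against 20% for the number actually analysed, and state the sidedness. For one-sided 5% this means 8 or more of 18 (error 1.6%, power 87.2%) or 9 or more of 24 (error 3.6%, power 97.3%). Name the same test in Section 8.3.
- **Section 8.1:** state a prespecified number at which enrolment closes, within the existing plan of about 24 screened and enrolled, and say that it applies regardless of observed responses. That figure includes screen failures, so it should not be read as 24 people dosed; dosing 24 would mean screening more than 24.
- **Sections 9.1 and 9.2:** limit periodic reviews to safety and data quality, so that they agree with the single end-of-study review in Section 9.6.

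The cost is wording. Power stays above the planned 80% at 18 and at 24. What is given up is the freedom to choose when to close after seeing responses, and a threshold of 5 that is easier to reach.
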